#### **3.5.7 Prior and Concomitant Treatments**

If the use of any concomitant treatment(s) becomes necessary, the treatment(s) must be recorded in the eCRF, including the name of the drug or treatment, dose, route of administration, date and time of the treatment, and indication. In the event that concomitant medication is administered, the

principal investigator or qualified sub-investigator must assess the subject's eligibility of continuing the participation in the study.

The following medications/therapies are not allowed to be taken/used by subjects enrolled in this study during the trial (by 6-month follow-up visit):

- Any pain medication for osteoarthritis except rescue medication (< acetaminophen 3.25 g per day or narcotic pain medications per investigator discretion in the case all other pain control measures have failed. Any pain medication other than acetaminophen 3.25g should only be used as last resort and only for a very limited time until symptoms can be controlled by more conservative methods).
- Any other injections or invasive procedures (including intra-articular injections) in the affected joint
- Any investigational drug (including placebo)
- Any therapy that may affect osteoarthritis, in the judgment of the investigator
- Lidocaine or other numbing agents while making the injection

After the completion of the 6-month follow-up visit, subjects may take pain medication for osteoarthritis and all medications will be tracked and recorded. Until the subjects complete the 12-month follow-up visit, any other treatments/therapies including surgeries (e.g. artificial joint replacement surgery) that, in the judgment of the investigator, affect the assessment of osteoarthritis will be prohibited.

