##### **3.2.1 Inclusion Criteria**

- 1) Subject who can give written informed consent
- 2) Male or female of any race, aged 22-60
- 3) Subject who had osteoarthritis of knee diagnosed at least six months prior to Screening
- 4) Subject who has joint pain  $\geq$  40mm on VAS (Visual Analog Scale) at Screening
- 5) Subject who has swelling, tenderness and active range of motion  $\geq$  Grade I at Screening
- 6) Subject who seeks invasive interventions of intra-articular injections
- 7) Subject who is willing to discontinue all pain medications for osteoarthritis except rescue medication (< acetaminophen 3.25 g per day) at least 72 hours prior to screening and throughout the duration of study
- 8) Subject who has radiographic evidence of grade 3 to 4 osteoarthritis based on the Kellgren and Lawrence radiographic criteria.
- 9) Female subject who meets one of the following criteria
  - a. Female subject of non-childbearing potential:
    - Post-menopausal for at least 6 months; or
    - Surgically sterile

b. Female patients of child-bearing potential:

- Neither pregnant nor lactating; and
- Abstinent or use adequate contraception (2 forms of birth control, one of which must be a barrier method)

10) Subject who is able to comply with lifestyle guidelines, scheduled visits, treatment plan, laboratory tests, and other study procedures

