### **3.3 Removal of Subjects from Study**

Subjects may be withdrawn from the study for the following reasons:

- At their own request or at the request of their legally acceptable representative
- If, in the investigator's opinion, continuation in the study would be detrimental to the subject's well-being
- At the specific request of the sponsor

Also, subjects must be withdrawn for the following reasons:

- A significant violation of the protocol, as determined by the sponsor or the investigator
- Highly significant abnormalities in the laboratory results (Highly significant abnormalities generally follow lab related exclusion criteria, but a PI can determine the high significance on any abnormalities for the safety of subject)
- Use of any other investigational drugs (including placebo)
- Subjects enrolled in the current trial but taking any prohibited medication/therapy stated in the inclusion/exclusion criteria that, in the investigator's opinion, will interfere with the study outcome.
- Subject enrolled in the current trial but having a baby

If a subject prematurely withdraws from the study, the subject must return to the clinical site for the early termination visit. In all cases, the reason for withdrawal must be recorded in the electronic Case Report Form (eCRF) and in the subject's medical records.

Contact will be maintained with subjects who are removed due to an adverse event (AE) until it has been resolved or stabilized, and the information will be documented in the eCRF and in the subject's medical records.

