#### **3.5.3 End of Study**

The efficacy results will be analyzed when the last subject completes Visit 6 (6-month follow-up) and this study is finished when the last subject completes Visit 8 (12-month follow-up).

Long-term follow-up visit will be conducted to collect long-term feedbacks (records of medications and treatments) following 2 years after injection for all subjects who complete 6-month visit and accept the long-term follow-up visit.

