6.2 SECONDARY EFFICACY ANALYSIS

6.2.1 WOMAC Score

WOMAC score will be collected at Visits 3, 4, 5, 6, 7 and 8 (Baseline, M1, M3, M6, M9 and M12) or Early Termination (only if the subject is early terminated after Visit 3) or Final Follow-up Visit. Summary statistics of WOMAC score will be presented by visit and treatment group. The change from baseline will also be calculated and represented in summary table.

① Change of WOMAC score from baseline at Month 6 (JointStem group vs. positive control group)

This secondary efficacy endpoint will be analyzed with an ANCOVA with factors of treatment and the baseline of WOMAC score as a covariate. Model-based LS Means of the differences between study and control groups, along with 95% CI and p-value will be provided.

② Change of WOMAC score from baseline at Months 9 and 12 (JointStem group)

Change of WOMAC score from baseline at Months 9 and 12 will be analyzed using paired t-test (two-sided test, $\alpha=0.05$) with the null hypothesis equal to zero. The number of patients, mean, standard deviation, minimum (min) and maximum (max) values for the baseline, months 9, months 12 and change from baseline will be calculated and reported in summary table. The p-value will also be provided. Shapiro-Wilks test will be used to test the normality of change of WOMAC score from baseline at Months 9 and 12. If change of WOMAC score from baseline at Months 9 and 12 doesn't satisfy normal distribution, Wilcoxon signed rank test will be performed.

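### Month 9 and 12 symptom scores may be taken on pain medication that inclusion 7 excludes, yet are tested against a medication-restricted baseline with no rule for analgesic use

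*Protocol*

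**What the plan says.** Inclusion 7 (Protocol Synopsis and 3.2.1) admits subjects willing to stop osteoarthritis pain medication, other than limited acetaminophen, "at least 72 hours prior to screening and throughout the duration of study". Protocol 3.5.3 sets the end point of that period: "this study is finished when the last subject completes Visit 8 (12-month follow-up". Protocol 3.3 makes withdrawal mandatory for "taking any prohibited medication/therapy stated in the inclusion/exclusion criteria" when the investigator judges that it will interfere with the outcome, and gives no Month 6 limit.

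Protocol 3.5.7 is narrower in time. Its listed medications are "not allowed to be taken/used by subjects enrolled in this study during the trial (by 6-month follow-up visit", and it then states: "After the completion of the 6-month follow-up visit, subjects may take pain medication for osteoarthritis", with use to be recorded. Other treatments that affect the assessment of osteoarthritis stay prohibited to Month 12, so pain medication is the item released. No washout before Visits 7 and 8 is stated (4.2.7, 4.2.8).

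On the analysis side, SAP 6.2.1 says "Change of WOMAC score from baseline at Months 9 and 12 will be analyzed using paired t-test", and SAP 6.2.2 and 6.2.4 to 6.2.7 do the same for VAS, Lysholm, KOOS, IKDC and RAND-36. Only JointStem subjects attend these visits, after unblinding. SAP 5.2 tabulates medications in the safety population, and SAP 2.4 carries the last observation forward for missing efficacy values. Neither says how a score taken on pain medication is handled.

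**The concern.** Two problems follow. First, a site cannot tell whether a subject who takes an analgesic at Month 9 is compliant (3.5.7) or is to be considered for withdrawal (inclusion 7 with 3.3). The answer changes the data: in one case an on-medication score enters the test, in the other the later visits are missing and an earlier value may be carried forward.

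Second, if 3.5.7 is followed, the two ends of the late comparison are measured under different conditions. Baseline is restricted; Months 9 and 12 are not. With no control arm at those visits, nothing in the design separates drug relief from product effect. The Month 9 and 12 tests are the plan's only secondary evidence on whether symptom improvement lasts, and they could be positive when nothing has lasted.

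**Working it through.** **Passages side by side**

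| Question | Inclusion 7 with 3.3 and 3.5.3 | Protocol 3.5.7 |
|---|---|---|
| Osteoarthritis pain medication between Month 6 and Month 12 | Restricted, and may lead to withdrawal | Allowed and recorded |
| Condition at baseline (Visit 3) | Restricted | Restricted |

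The plan gives no power calculation or effect figure to reproduce. The only stated number is n = 30 split 20 and 10, which agrees with 2:1 (30 × 2/3 = 20). What follows is an illustration.

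**Inputs**
- n = 20 JointStem subjects (Protocol 6.2; SAP 1.3.3).
- Paired t-test, two-sided 5% (SAP 6.2.1, 6.2.2).
- Assumed, not in the documents: true product effect at Month 9 or 12 of zero; SD of change 22 mm on the 100 mm VAS; analgesic relief of 10 to 20 mm; 40% or 60% of subjects using analgesics, unrelated to outcome.

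Improvement is counted as positive below.

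**Step 1: what the test needs.** The critical value is t(0.975, 19 df) = 2.093. The standard error is 22/√20 = 4.92 mm. An observed mean change of 2.093 × 4.92 = 10.3 mm, or 0.47 SD, is significant. With no shift, the chance of significant improvement is 2.5%.

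**Step 2: uniform shift.** Mean shift = share of users × relief; non-centrality = shift / 4.92; probability from the noncentral t with 19 df.
- 40% users: shift 4 to 8 mm, non-centrality 0.81 to 1.63, probability 0.118 to 0.339.
- 60% users: shift 6 to 12 mm, non-centrality 1.22 to 2.44, probability 0.211 to 0.639.

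**Step 3: users and non-users mixed.** Step 2 overstates the upper end, because relief in only some subjects also widens the SD. The variance becomes SD² + share × (1 − share) × relief². For 40% users and 20 mm this is 484 + 0.24 × 400 = 580, an SD of 24.1 mm. Simulating the mixture (200,000 trials per cell) gives:

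| Users | 10 mm | 15 mm | 20 mm |
|---|---|---|---|
| 40% | 11.5% | 19.4% | 28.9% |
| 60% | 20.4% | 38.0% | 55.9% |

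**Step 4: sensitivity to the SD.** For relief of 10 to 20 mm, the same simulation at SD 30 mm gives 8% to 19% (40% users) and 13% to 37% (60%). At SD 15 mm it gives 19% to 47% and 36% to 81%.

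**Step 5: scale-free version.** For the other scales, in units of the SD of change, 50% users with relief of 0.5 SD gives 17.7% and with 0.8 SD gives 35.0% (simulated mixture).

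**The case against.** The strongest case for the plan has four parts.

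- *Inclusion 7 is an entry criterion about willingness, and 3.5.7 is the operative rule.* That is a reasonable reading, but inclusion 7 runs for the duration of the study and 3.3 ties mandatory withdrawal to what the inclusion and exclusion criteria prohibit. The texts still need reconciling, and the analysis gap is present under the 3.5.7 reading in any case.
- *The endpoints are secondary, in a small study that describes itself as proof of concept.* This stands, and limits the weight of the point. The late changes are also uncontrolled and open-label, so attribution to JointStem is weak even without analgesics. Medication differences add a further bias, one that recorded data can partly address.
- *The size is assumed.* Also true. The documents give no SD, relief or usage figure; only the direction is secure, and only if analgesics are used and work.
- *Medication is recorded, so readers can check.* A count by drug class is not linked to the scores, and an unplanned check carries little weight.

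Two stronger readings are tempting. A reader might infer that the Month 6 co-primary tests are biased in the same way, because 3.5.7 allows "narcotic pain medications per investigator discretion in the case all other pain control measures have failed". The documents do not support this. The list in 3.5.7 covers enrolled subjects up to the Month 6 visit, so baseline and Month 6 fall under the same rule; narcotics are confined to a brief last resort; and concomitant medication triggers a review of continued participation. The restricted-versus-released contrast is absent there. A reader might also infer that the plan will declare a lasting effect. The SAP attaches worded conclusions only to the Month 6 primary tests, so the late results can be misread but are not bound to be.

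**Conclusion.** The point holds for the Month 9 and 12 symptom scores: WOMAC, VAS, Lysholm, KOOS, IKDC and RAND-36. The contradiction between inclusion 7, 3.3 and 3.5.7, and the absence of any rule for on-medication scores, are certain from the text. The size is illustrative: a false late improvement in about 12% to 29% of trials at 40% users and about 20% to 56% at 60%, against 2.5%. That rests on n = 20, SD 22 mm, relief of 10 to 20 mm, no product effect, and use unrelated to outcome. The Month 6 tests are not subject to the post-Month 6 release, and the Month 12 MRI reading is not a symptom score. This should be corrected, but it does not threaten the primary analysis.

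**What to change.** 1. Reconcile inclusion 7 (Synopsis and 3.2.1), 3.3 and 3.5.7 on osteoarthritis pain medication after Month 6. Which rule is right is for the sponsor and investigators.
2. In SAP 6.2.1, 6.2.2 and 6.2.4 to 6.2.7, keep the as-observed Month 9 and 12 tests and add a pre-specified companion analysis. A score taken on osteoarthritis pain medication beyond the acetaminophen allowance in force at baseline, within a stated window before the visit, is replaced by the worse of the baseline and observed score, in the direction of each scale.
3. Describe an effect as lasting only if both analyses agree.
4. State that the Month 9 and 12 changes are uncontrolled and cannot be attributed to JointStem alone.

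Setting on-medication scores to baseline looks simpler but can flatter the product, because it erases worsening. In an extreme case where the worst-off 40% are the users (SD 22 mm, relief 10 to 20 mm), the as-observed test is falsely positive in 20% to 57% of trials and the set-to-baseline test in 79%, with a spurious mean gain of 8 mm. The worse-of rule never credits improvement over baseline to an on-medication score and never makes a score more favourable than the one recorded. It is not a complete cure: in that same case it still gives 15% to 39%, because relief can hide worsening. With use unrelated to outcome it gives about 1%.

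The cost is slightly more analysis of data already recorded, and late estimates that are less favourable, including for subjects with a real benefit who also took an analgesic.

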5.2 PRIOR AND CONCOMITANT THERAPY

Prior medications are defined as medications that started prior to the intra-articular injection of study drug. Concomitant medications are defined as medications (other than the study drug) taken on or after the intra-articular injection of the study drug during the study. Medications started before the dose of study drug and continuing at the time of the intra-articular injection of study drug are considered both prior medication and concomitant medication.

All investigator terms for medications recorded on the CRF will be coded using the World Health Organization (WHO) Anatomical Therapeutic Chemical (ATC) drug dictionary (Version Dec 2015, WHODDE). The number (percentage) of subjects who took prior and concomitant medications will be summarized in the safety population, by ATC Classification, WHO Drug PT, treatment group and total.

A subject data listing of prior and concomitant therapy will be provided.

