6.2.2 VAS Score

VAS score will be collected at Visits 3, 4, 5, 6, 7 and 8 (Baseline, M1, M3, M6, M9 and M12) or Early Termination (only if the subject is early terminated after Visit 3) or Final Follow-up Visit. Summary statistics of VAS score will be presented by visit and treatment group. The change from baseline will also be calculated and represented in summary table.

- ① Change of VAS score from baseline at Month 6 (JointStem group vs. positive control group)

This secondary efficacy endpoint will be analyzed with an ANCOVA with factors of treatment and the baseline of VAS score as a covariate. Model-based LS Means of the differences between study and control groups, along with 95% CI and p-value will be provided.

- ② Change of VAS score from baseline at Months 9 and 12 (JointStem group)

Change of VAS score from baseline at Months 9 and 12 will be analyzed using paired t-test (two-sided test, $\alpha=0.05$) with the null hypothesis equal to zero. The number of patients, mean, standard deviation, minimum (min) and maximum (max) values for the baseline, months 9, months 12 and change from baseline will be calculated and reported in summary table. The p-value will also be provided. Shapiro-Wilks test will be used to test the normality of change of VAS score from baseline at Months 9 and 12. If change of VAS score from baseline at Months 9 and 12 doesn't satisfy normal distribution, Wilcoxon signed rank test will be performed.

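### The pain-medication rules conflict for Months 6 to 12, and the Month 9 and 12 symptom tests cannot separate a lasting JointStem effect from newly permitted pain medication

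*Protocol*

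**What the plan says.** **The medication rule.** Protocol 3.2.1, inclusion 7 (repeated in the synopsis), requires willingness to "discontinue all pain medications for osteoarthritis except rescue medication (< acetaminophen 3.25 g per day") and fixes the period as "at least 72 hours prior to screening and throughout the duration of study". Protocol 3.5.3 says "this study is finished when the last subject completes Visit 8 (12-month follow-up"), that is, Month 12. Protocol 3.5.7 limits its own list of prohibited medication to the period up to the 6-month visit and then states: "After the completion of the 6-month follow-up visit, subjects may take pain medication for osteoarthritis and all medications will be tracked and recorded".

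**Withdrawal.** Protocol 3.3 lists among the mandatory reasons "taking any prohibited medication/therapy stated in the inclusion/exclusion criteria", with the condition that the investigator believes it will interfere with the outcome.

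**Analysis.** SAP 6.2.1 states "Change of WOMAC score from baseline at Months 9 and 12 will be analyzed using paired t-test" and SAP 6.2.2 states "Change of VAS score from baseline at Months 9 and 12 will be analyzed using paired t-test". SAP 6.2.4 to 6.2.7 do the same for Lysholm, KOOS, IKDC and RAND-36. All are two-sided 5% tests against zero, with a Wilcoxon signed rank test if normality fails. Only JointStem subjects attend Visits 7 and 8 (protocol 3.5.8, 4.2.7 and 4.2.8).

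**Use of the medication record.** SAP 5.2 defines concomitant medication as that "taken on or after the intra-articular injection of the study drug during the study" and provides a table by treatment group and a listing. SAP 2.4 covers missing efficacy values by LOCF.

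**The concern.** There are two linked problems.

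First, the protocol gives two answers on whether a JointStem subject may take osteoarthritis pain medication between Month 6 and Month 12. Two sites could handle the same Month 8 analgesic differently. One records it and keeps the subject. The other may judge that 3.3 requires withdrawal, in which case the missing Month 9 and 12 scores fall to LOCF.

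Second, if 3.5.7 is followed, the measuring conditions change after Month 6. Baseline (Visit 3) and Month 6 scores fall in the restricted period; Month 9 and 12 scores may not. With no control arm at those visits, nothing absorbs the shift. A subject whose benefit has faded and who starts an analgesic can score as improved from baseline. The Month 9 and 12 tests are the planned symptom evidence on duration of effect, so an unqualified significant result there would be easy to over-read.

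A smaller consequence concerns SAP 5.2. Its table covers follow-up to Month 12 for JointStem and to Month 6 for control, so the arms are not compared over the same period or under the same rule.

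**Working it through.** **1. The texts side by side, Months 6 to 12**

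| Source | Pain medication beyond rescue, after Month 6 |
|---|---|
| Inclusion 7 with 3.5.3 | restricted until Month 12 |
| 3.5.7 | permitted and recorded |
| 3.3 | withdrawal if prohibited by the entry criteria and judged to interfere |

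One might read 3.5.7 as defining the trial as ending at Month 6. But 3.5.3 ends the study at Visit 8, and 3.5.7 itself keeps other treatments prohibited until the 12-month visit. The conflict remains.

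**2. Does the SAP use the medication record in the efficacy analysis?** No. SAP 5.2 tabulates and lists it, SAP 2.4 deals only with missing values, and SAP 6.2.1, 6.2.2 and 6.2.4 to 6.2.7 contain no covariate, intercurrent-event rule or sensitivity analysis for scores taken on pain medication.

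**3. Possible size.** The plan has no power figure to reproduce: 30 subjects are predefined, and 2:1 gives 20 and 10 (protocol 6.2). Inputs from the documents are n = 20 and two-sided α = 0.05. Assumed inputs are no true JointStem effect, a fraction f of subjects using analgesics, and an improvement of e in users, in units of the SD of change among non-users.

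- Mean shift = f × e
- SD of the mixture = √(1 + f(1 − f)e²)
- Noncentrality = √20 × f × e / SD
- P(false improvement) = P(noncentral t with 19 df > 2.093)

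Example, f = 0.5 and e = 0.5: shift 0.25; SD = √1.0625 = 1.031; noncentrality = 4.472 × 0.25 / 1.031 = 1.085; probability 17.6%.

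| Share using | e = 0.3 | e = 0.5 | e = 0.8 |
|---|---|---|---|
| 25% | 5.0% | 7.5% | 12.4% |
| 50% | 9.2% | 17.6% | 35.1% |
| 75% | 15.6% | 34.3% | 67.2% |

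The nominal rate in this direction is 2.5%. A simulation of 20,000 trials that does not treat the mixture as normal gave 8.9%, 17.2% and 35.2% for the 50% row.

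**4. Would setting users to zero change repair this?** Only if use is unrelated to outcome. With n = 20, true mean change zero and half using, simulated false improvement under that rule is about 2% when use is random. It is about 9%, 21% and 44% when the correlation between the tendency to use and worsening is 0.3, 0.5 and 0.7. Subjects who are worse than baseline are reset to zero, which flatters the mean. Also requiring the as-observed test to succeed still passes about 7% to 18% at correlation 0.5 and e from 0.3 to 0.8.

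**5. Counting users as not improved.** This can only lower the favourable statistic relative to the subjects' medication-free scores, so it cannot create false improvement. It is strict at n = 20:

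- Worst rank in the signed rank test: the favourable rank sum must reach 158 of 210. With k users holding the top k ranks, its maximum is (20 − k)(21 − k)/2, which is 171 for k = 2 and 153 for k = 3. Three users therefore rule out significance.
- Sign test: at least 15 of 20 must improve (upper tail 21,700/1,048,576 = 2.1%). Up to five users can be accommodated.

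**The case against.** The strongest reply is that inclusion 7 is an entry criterion about willingness, while 3.5.7 is the specific conduct rule with its own period and should govern. Section 3.5.7 also requires the investigator to reassess participation whenever concomitant medication is given, and medication is recorded. These are secondary tests in a study described as proof of concept, and the usage and effect figures above are assumptions. Much of this stands, and it limits the point to secondary analyses. It does not remove the conflict, because 3.3 refers back to the entry criteria. Nor does it fill the gap in the SAP, because the record never enters the efficacy analysis.

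A reader might infer more than the documents support:

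- *That baseline is off medication and later scores are on it.* Rescue acetaminophen is allowed throughout, 3.5.7 also allows last-resort narcotics before Month 6, and no rescue washout before post-screening visits is stated. The contrast is between more and less restricted use, and 3.5.7 says only that subjects may take medication.
- *That any analgesic after Month 6 forces withdrawal.* Section 3.3 applies only if the investigator thinks it will interfere.
- *That these tests are the only evidence of durability.* The Month 6 to Month 12 MRI comparison is not a symptom score, and the protocol plans an exploratory Month 24 comparison between arms that includes treatment and medication history.
- *That the plan explicitly credits the Month 9 and 12 change to JointStem.* Explicit conclusions are written only for the Month 6 co-primaries. The later attribution is implied by testing an efficacy endpoint in one arm against zero.
- *That the medication table must show more analgesic use on JointStem.* Longer follow-up under a looser rule makes this likely, but it depends on actual use.

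**Conclusion.** The point holds in a limited form. The protocol contradicts itself on osteoarthritis pain medication between Months 6 and 12; which rule is right is for the clinical team. If 3.5.7 is followed, the Month 9 and 12 within-group tests of WOMAC, VAS, Lysholm, KOOS, IKDC and RAND-36 cannot separate a lasting JointStem effect from the effect of newly permitted medication.

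How far this matters depends on how many subjects use such medication and how well it works, and the documents give neither. Under the stated assumptions false improvement runs from about 5% to 12% with a quarter using and 9% to 35% with half using, against 2.5%. If nobody uses it, there is no inflation from this source.

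The Month 6 co-primaries, the Month 6 between-group comparisons and the Month 6 within-group tests precede the permission and are not affected by it. This should be corrected, but it does not threaten the primary result.

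**What to change.** 1. **Protocol.** The clinical team reconciles inclusion 7, 3.3 and 3.5.7 for Months 6 to 12. The same text should settle what was permitted at baseline, since inclusion 7 and 3.5.7 differ on last-resort narcotics.
2. **SAP 6.2.1, 6.2.2 and 6.2.4 to 6.2.7, Months 9 and 12.** Keep the as-observed test. Beside it, pre-specify a composite sensitivity analysis: a subject with recorded osteoarthritis pain medication beyond that permitted at baseline, within a window before the assessment fixed in advance of the analysis, counts as not improved. Worst rank or a count of improved against not improved would both serve; zero change would not. Name the form in advance, because at n = 20 three users block the worst-rank version while the sign test accommodates up to five. Label the Month 9 and 12 results as uncontrolled, and claim lasting symptom benefit only if both analyses agree.
3. **SAP 5.2.** Tabulate concomitant medication separately from injection to Visit 6 (both arms) and after Visit 6 (JointStem only).

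**Cost.** SAP wording, one added analysis per scale and one split table. No new data are needed, because 3.5.7 already requires drug, dose, date and time to be recorded. The sensitivity result is deliberately conservative, may fail even when a real effect persists, and may make the Month 9 and 12 results look less favourable.
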